1 **Prevalence and determinants of home accidents among Turkish older men and women**

2 **Abstract**

3 **Background:** Home accidents are a significant public health issue in developed and developing
4 countries. The present study aims to identify the factors associated with home accidents among
5 older individuals in Türkiye.

6 **Methods:** Microdata obtained from the Türkiye Health Survey conducted by the Turkish
7 Statistical Institute (TUIK) in 2019 and 2022 were utilized in the present study. Binary logistic
8 regression analysis was used to determine factors influencing home accidents.

9 **Results:**

10 **Conclusion:**

11 **Keywords:** Older individuals, home accident, discrete choice model, binary logistic regression,
12 Türkiye

13

14 **1. Introduction**

15 Home accidents are a significant public health issue in developed and developing countries (1).
16 Home refers to where older individuals spend most of their daily time, thus increasing their
17 likelihood of experiencing any accidents at home. Home accidents are more common among
18 older individuals and can lead to serious health consequences (2). Individuals aged 65 and
19 above are particularly at high risk of home accidents due to physical, psychological, and social
20 impairments. Musculoskeletal problems and sensory and motor function loss in this group
21 increase the risk of accidents (3). Home accidents are assumed to be unintentional and can range
22 from minor injuries to fatalities. These accidents can occur within the home and in surrounding
23 areas such as garages, gardens, terraces, and stairs (4). While unintentional home and

24 recreational injuries pose a risk for individuals aged 85 and older, outdoor injuries also pose a
25 risk for younger, older individuals (aged 75-79) (5).

26 Home accidents represent a significant health problem in terms of morbidity and mortality at
27 older ages (6). The frequency of home accidents is found to be three times higher in women,
28 2.7 times higher in individuals living with children, 2.3 times higher in visually impaired older
29 individuals, and 2.7 times higher in older individuals with poor health status. Moreover,
30 advancing age is considered a risk factor for home accidents (7). Various home accidents
31 include falls, burns, crushes, cuts, and electric shocks (8). Around 80% of injuries that
32 necessitate medical attention take place within the home environment, with a significant portion
33 of these injuries, approximately two-thirds, being classified as serious injuries, predominantly
34 resulting from falls and burns (5).

35 Similar to the global trend, the older population in Türkiye is rapidly increasing (9). While the
36 global average older population ratio was 9.9% in 2022, Türkiye's older population ratio of
37 9.8% is close to the global average (10). These data indicate that Türkiye has a significantly
38 more ageing population (11). The prevalence of older individuals experiencing at least one
39 accident in Türkiye is 38.6%, with falls being the most common accident at 63.3% (6). As
40 reported in another study, more than half of the older population had experienced a home
41 accident in the previous year (59.4%), with falls (70.2%) and kitchen accidents (31.7%) ranking
42 at the top (12). Epidemiological characteristics of injured patients were examined in Tehran,
43 where traffic accidents and falls were identified as the two most common causes of injury (13).

44 Falls in the home environment account for over 33% of accidents and are the second leading
45 cause of death and the main cause of injury in more than 41.2% of cases. Falls during patient
46 admissions also impose additional burdens and costs on the healthcare system (14). The total
47 medical cost for treating fatal and non-fatal fall injuries in older adults exceeded \$50 billion in
48 the USA in 2015 (15). "Falls" occurring in the bathroom, hallway, living room, or bedroom,

49 originating from the floor or stairs, can result in doctor visits and hospitalizations (1). Factors
50 contributing to increased home injuries include advanced age, economic hardships, obesity, and
51 comorbidities (5). Among older adults living in the community, a significant proportion of falls,
52 ranging from 10% to 38%, lead to non-fatal injuries, hospitalizations, disability, or a decline in
53 independence (16-18). Various risk factors have been identified in association with falls,
54 including advanced age, a history of previous falls, muscle weakness, difficulties with walking
55 and balance, dementia, impaired vision, arthrosis, diabetes, stroke, Parkinson's disease, and
56 urinary incontinence (19).

57 Burns constitute another type of home accident in older individuals. Burn injury is one of the
58 most devastating types of trauma affecting millions of people worldwide, leading to severe
59 morbidity and mortality, with individuals aged 65 and above being the most affected
60 demographic group. The presence of comorbidities in older individuals leads to higher
61 morbidity and mortality in burns due to age-related changes in the central and peripheral
62 nervous system (20).

63 Older individuals may also experience traumas as a result of accidents that occur within their
64 homes. These traumas can have severe consequences for older adults, leading to increased rates
65 of illness and death (21). The proportion of older individuals presenting to Level I and II trauma
66 centers was 23% in 2003, which increased to 30% in 2009 (22). This rate is expected to reach
67 39% by 2050 (23). The cost of home accidents is estimated to be 3.5 times higher than that of
68 traffic accidents (24).

69 Decreased capacities of older individuals often result in limitations in daily life activities.
70 Ageing and declining individual capacities increase the prevalence of disease and disability
71 among older individuals. Living at home, associated with independence and autonomy-related
72 physical, psychological, and psychosocial benefits, is a desired and essential goal for older
73 individuals (25). Therefore, it is necessary to examine the factors contributing to home

74 accidents among older individuals to ensure home safety. Hence, this study investigates the risk
75 factors affecting home accidents among older individuals in Türkiye.

76 **2. Method**

77 This section will explain the specifics of the data utilized in the research, the variables
78 categorized as dependent and independent, and the methodology employed in the study.

79 **2.1. Data**

80 The research utilised microdata from the Türkiye Health Survey, published by the Turkish
81 Statistical Institute (TUIK) in 2019 and 2022. The most recent data available from TUIK's
82 health survey is 2022. The Türkiye Health Survey is a significant research endeavour that
83 reflects the entire country and enables national and international comparisons. The dataset
84 offers a wide range of health indicators related to the well-being of infants, children, and adults,
85 along with insights into individuals' access to healthcare services (26).

86 **2.2. Outcome Variables**

87 Older individuals are at risk for home accidents due to their developmental characteristics (2,
88 3).

89 The data obtained from individuals aged 60 and above were used in this study. The study's
90 dependent variable is the occurrence of home accidents, measured by the question, "Have you
91 experienced a home accident resulting in injury in the last 12 months? (Yes, No)." In the
92 established model, the dependent variable categories are assigned 1 if the individual has
93 experienced a home accident and 0 if they have not.

94 **2.3. Independent variables**

95 The independent variables included in the study are those available in the Türkiye Health
96 Survey. These variables were selected as risk factors based on the literature (5, 7, 19, 27-33).

97 The independent variables of this study are gender (female, male), education level (illiterate/less
98 than primary school, primary school, secondary school and above), marital status (single,
99 married), employment status (unemployed, employed), general health status (very good/good,
100 fair, poor/very poor), presence of arthrosis (no, yes), urinary incontinence (no, yes), wearing
101 glasses (yes/cannot see at all, no), experiencing difficulty in carrying or holding items (no
102 difficulty, some difficulty/considerable difficulty/cannot do at all), experiencing difficulty in
103 affording health care services (no, yes), and survey year (2019, 2022).

104 **2.4. Statistical Analysis**

105 Survey statistics in Stata 15 (Stata Corporation) were utilized to address the complex sampling
106 design and weights. Weighted analysis was conducted. Initially, frequencies and percentages
107 were obtained considering the home accident occurrence and years among the older
108 participants. Then, binary logistic regression analyses were employed to identify the risk factors
109 influencing home accidents in older individuals.

110 **3. Results**

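### Nine of the 17 risk factors that the Introduction takes from three of the plan's selection sources, age among them, are missing from the model without a stated reason, so the retained odds ratios are open to residual confounding

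*Combined protocol and SAP*

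**What the plan says.** Section 2.3 (Independent variables) gives two rules for the covariates. One is availability: "The independent variables included in the study are those available in the Türkiye Health" Survey. The other is prior evidence: "These variables were selected as risk factors based on the literature (5, 7, 19, 27-33"). It then lists gender, education, marital status, employment, general health, arthrosis, urinary incontinence, wearing glasses, difficulty carrying or holding items, difficulty affording health care, and survey year.

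The Introduction reports what three of those sources found:

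- Source 5: the factors "contributing to increased home injuries include advanced age, economic hardships, obesity, and" comorbidities.
- Source 7: accident frequency is three times higher in women, "2.7 times higher in individuals living with children, 2.3 times higher in visually impaired older" people, and 2.7 times higher with poor health. It adds that "advancing age is considered a risk factor for home accidents (7").
- Source 19, on falls: risk factors "including advanced age, a history of previous falls, muscle weakness, difficulties with walking" "and balance, dementia, impaired vision, arthrosis, diabetes, stroke, Parkinson's disease, and" urinary incontinence.

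Section 2.1 says of the dataset that it "offers a wide range of health indicators related to the well-being of infants, children, and adults". Section 2.2 uses age only as an entry criterion (60 and above). Section 2.4 says the logistic regressions are meant to identify risk factors. It names no primary exposure and no adjustment set.

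**The concern.** The study exists to say which characteristics are associated with home accidents. The model departs from its own evidence base without explanation, and several of the missing factors plausibly travel with those kept. Age may go with marital status, employment, arthrosis and incontinence. Diabetes or stroke may go with poor general health and incontinence. Living with children may go with marital status, and walking difficulty with arthrosis and carrying difficulty.

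Where such a link exists and the missing factor affects accidents, the odds ratio of the retained variable takes up part of that effect. The paper could then name a correlate as a determinant. Carrying difficulty is the clearest risk: it is the only functional limitation in the model, while source 19 names walking and balance.

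**Working it through.** The plan states no figure on this point to reproduce. The check has two parts.

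**1. Factors named against factors modelled.** Inputs are the Introduction's statements on sources 5, 7 and 19 and the list in section 2.3. The multipliers are credited to source 7 because its citation closes that pair of sentences.

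| Status in the model | Factors | Count |
|---|---|---|
| Entered directly | female sex (7), poor general health (7), arthrosis (19), urinary incontinence (19) | 4 |
| Proxy or partial | vision, through glasses (7, 19); economic hardship, through affording care (5); muscle weakness, through carrying or holding (19); comorbidities in general (5) | 4 |
| Absent | age (5, 7, 19), obesity (5), living with children (7), previous falls, walking or balance difficulty, dementia, diabetes, stroke, Parkinson's disease (all 19) | 9 |

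- Total: 4 + 4 + 9 = 17.
- Absent: 9/17 = 53%. Without the generic comorbidities entry, 9/16 = 56%.
- Absent or only partly measured: 13/17 = 76%.

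Age is the only factor named by all three sources. Because eligibility is set by age, the microdata must hold it in some form.

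**2. What one omitted factor could do.** For a covariate with no effect of its own, the apparent ratio is

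B = [1 + p1(R − 1)] / [1 + p0(R − 1)],

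where R is the omitted factor's ratio, and p1 and p0 are its prevalence in people with and without the covariate. R = 2.7 is the Introduction's figure for living with children. R = 1.5 and 2.0 are assumed, and so are all the prevalences. Here p0 = 20%.

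| R | p1 = 20% | 30% | 40% | 50% | 60% |
|---|---|---|---|---|---|
| 1.5 | 1.00 | 1.05 | 1.09 | 1.14 | 1.18 |
| 2.0 | 1.00 | 1.08 | 1.17 | 1.25 | 1.33 |
| 2.7 | 1.00 | 1.13 | 1.25 | 1.38 | 1.51 |

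Example: R = 2.7 and p1 = 40% give (1 + 0.40 × 1.7)/(1 + 0.20 × 1.7) = 1.68/1.34 = 1.25.

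If the imbalance runs the other way the bias falls below 1. With p1 = 20%, p0 = 30% and R = 2.7, B = 1.34/1.51 = 0.89.

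The formula is on the risk-ratio scale and treats one factor at a time. The imbalance that matters is the one left after adjustment for the other covariates, which may be smaller than a crude one. The documents give none of these quantities.

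**The case against.** The strongest reply is availability. Section 2.3 limits the covariates to what the survey holds, and no passage shows that either wave records obesity, diabetes, stroke, walking difficulty or household composition. A reader might infer from the description of a broad dataset that these items were there and were passed over. The documents do not establish that. If an item is missing, its absence is a limitation to report and not a wrong choice. This stands for each of those items, but not for age.

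A reader might also infer that the odds ratios are confounded. The documents support only a risk. They give no joint distribution, the bias may be nil or go either way, and general health may already carry part of the comorbidity effect.

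Nor do they support a claim that most of the factors named by the selection sources are left out. Nine of 17 is a narrow majority for three of ten cited sources, and the text does not say what sources 27–33 name. It would also be wrong to say that comorbidity is ignored, since arthrosis and incontinence are modelled. Source 19 concerns falls, while the outcome is any injurious home accident, so its list need not be adopted whole.

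Finally, walking difficulty may lie on the path from arthrosis to accident, and adjusting for it could hide an association the study wants to find. This stands, and it shapes the fix. It does not justify the present list, because carrying difficulty and general health may equally be consequences of arthrosis and are already in the model.

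**Conclusion.** The point holds as a gap between the stated selection basis and the model: nine named factors are absent, with no reason given for any of them. Age is the firmest case, because all three sources name it and it must be recorded. The consequence is a risk of residual confounding in the retained odds ratios, of unknown size and direction. The illustrative range for a covariate with no effect is about 1.0 to 1.5. It rests on a single omitted factor with a ratio of 1.5 to 2.7, on assumed prevalences of 20% against 20% to 60%, and on an imbalance in the upward direction. It shows what is possible and does not estimate the bias in this study. The change is a worthwhile and cheap improvement, given that the aim is to identify determinants.

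**What to change.** In section 2.3:

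- Add age to the adjusted model, in whatever form the microdata hold it.
- Add obesity, diabetes, stroke and household composition (including living with children) where both the 2019 and 2022 microdata record them.
- Add walking difficulty, where both waves record it, in a sensitivity model only, because it may mediate the effect of arthrosis. Report the arthrosis and carrying-difficulty odds ratios with and without it.
- For each named factor that is not recorded in both waves, say so. Do not interpret its closest correlate, such as carrying difficulty, as an independent determinant.
- Give a one-line reason for any named factor that is recorded but still left out.

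No new data are needed. The cost is somewhat wider intervals and some records lost to item non-response. Neither can be sized here, because the documents give no sample size, event count or non-response figures.

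### Age is named as a risk factor and defines the sample, yet it is missing from the regression model without a stated reason, leaving the other odds ratios open to confounding by age

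*Combined protocol and SAP*

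**What the plan says.** Section 2.3 sets two rules for choosing covariates. The first is availability: "The independent variables included in the study are those available in the Türkiye Health" Survey. The second is prior evidence: "These variables were selected as risk factors based on the literature (5, 7, 19, 27-33"). The list then begins "The independent variables of this study are gender (female, male), education level (illiterate/less" and runs through marital status, employment, general health, arthrosis, urinary incontinence, glasses, difficulty carrying or holding items and difficulty affording care, ending with survey year. That is 11 variables, none of them age.

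Section 2.4 plans weighted frequencies by accident occurrence and year, then survey-weighted binary logistic regression. It mentions no adjustment, stratification or standardisation by age.

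The rest of the document treats age as important:

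- Introduction, reference 7: "advancing age is considered a risk factor for home accidents (7").
- Introduction, reference 5, on factors "contributing to increased home injuries include advanced age, economic hardships, obesity, and" comorbidities.
- Introduction, reference 19, on risk factors for falls, "including advanced age, a history of previous falls, muscle weakness, difficulties with walking" and balance, among others.
- Introduction, on the health covariates: "Ageing and declining individual capacities increase the prevalence of disease and disability".
- Section 2.2, on the sample: "The data obtained from individuals aged 60 and above were used in this study".

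**The concern.** The stated aim is to find the risk factors for home accidents in older people, and the title promises determinants. A model without an age term gives no odds ratio for a determinant that the document itself names three times.

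The second problem is confounding. If older people within the 60-and-over group have more accidents and also more arthrosis, incontinence and functional difficulty, part of the age effect will appear in the odds ratios of those conditions. A reader could not tell whether an odds ratio for incontinence reflects the condition or simply older age. Restricting the sample to 60 and over removes only part of the age variation. No upper limit is set, and the Introduction itself contrasts injury risk at 75-79 with that at 85 and older.

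**Working it through.** **1. What the model contains.** Non-intercept parameters from the categories in section 2.3: education 2, general health 2, and one each for gender, marital status, employment, arthrosis, incontinence, glasses, carrying difficulty, affordability and survey year. That is 2 + 2 + 9 = 13, none for age.

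**2. Do the plan's own rules explain the omission?**

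- Availability does not: selecting people aged 60 or over needs an age variable, at least in bands.
- Literature does not: references 5, 7 and 19 are cited in the Introduction for age and in section 2.3 for covariate choice.

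**3. Is the structure for confounding present?** The document links age to the outcome (references 5, 7, 19) and to disease and disability. Arthrosis, incontinence and carrying difficulty fall under the latter. For employment, education and marital status a link with age is plausible, but the document does not state one.

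**4. How large could the effect be?** The document gives no age distribution, accident rate by age, covariate prevalence or sample size, so there is no figure to reproduce. Everything below is assumed, for illustration.

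*Inputs.* Age shares are 55/32/13% for 60-69/70-79/80+. The exposure has no true effect and a prevalence of 8/15/30% across the bands.

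*Crude formula.* Risk in the exposed = Σ(share × prevalence × risk) / Σ(share × prevalence); for the unexposed, replace prevalence by 1 − prevalence. The odds ratio follows.

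*Worked case, accident risk 3/4.5/6%.*

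- Exposed weights: 0.55 × 0.08 = 0.044; 0.32 × 0.15 = 0.048; 0.13 × 0.30 = 0.039; total 0.131.
- Exposed risk: (0.044 × 0.03 + 0.048 × 0.045 + 0.039 × 0.06) / 0.131 = 0.00582 / 0.131 = 0.0444.
- Unexposed weights: 0.506, 0.272, 0.091; total 0.869.
- Unexposed risk: (0.506 × 0.03 + 0.272 × 0.045 + 0.091 × 0.06) / 0.869 = 0.03288 / 0.869 = 0.0378.
- Odds ratio: (0.0444/0.9556) / (0.0378/0.9622) = 1.18.

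*Adjusted version.* A population logistic model is fitted to the exposure, carrying difficulty (15/30/55%), poor health (15/25/40%) and employment (25/8/2%), with age left out. The covariates are independent within each age band and have no true effect.

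| Accident risk by age band | Age OR, 80+ vs 60-69 | Spurious OR, crude | Spurious OR, adjusted |
|---|---|---|---|
| flat | 1.00 | 1.00 | 1.00 |
| 4/4.5/5% | 1.26 | 1.05 | 1.04 |
| 4/5/6% | 1.53 | 1.10 | 1.08 |
| 3/4.5/6% | 2.06 | 1.18 | 1.15 |
| 3/5/9% | 3.20 | 1.31 | 1.25 |
| 3/6/12% | 4.41 | 1.42 | 1.33 |

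Varying the exposure gradient from 10/14/20% to 5/15/40% over the five non-flat patterns gives 1.03 to 1.70 crude and 1.02 to 1.55 adjusted.

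**5. Sensitivity to the other covariates having real effects.** Keep the same age-specific risks, but give carrying difficulty and poor health each an odds ratio of 1.5. The five adjusted values for the 8/15/30% exposure become 0.99, 1.03, 1.09, 1.19 and 1.26. With an odds ratio of 2 they become 0.95, 0.99, 1.05, 1.14 and 1.22. The extreme of 1.55 becomes 1.43 or 1.34.

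**The case against.** The strongest counter-argument is that age may act largely through variables already in the model. The Introduction attributes the high risk at 65 and over to impairments, and names musculoskeletal problems and loss of sensory and motor function. Arthrosis, carrying difficulty, glasses and general health partly stand in for these. The adjusted figures in the table give those covariates no effect, so they lean high. The sensitivity run shows that in the mildest patterns the bias can vanish or reverse. Only four of the 11 planned covariates are represented, and the largest figures need an assumed age odds ratio of 3.20 to 4.41, which nothing in the document supports. This stands as a criticism of any particular size. It does not justify the omission: mediation changes how the age odds ratio should be read, but does not stop age confounding the odds ratios of arthrosis or incontinence. Nor does the plan offer mediation as its reason.

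It can also be said that section 2.3 does not promise to include every cited factor; obesity, diabetes, stroke and living with children are left out too. That is true. Age differs because it is certainly held in some form and because the document links it both to the outcome and to the disease and disability covariates.

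Finally, the abstract speaks only of associated factors, for which confounding matters less. But the title speaks of determinants and section 2.4 of factors that influence accidents, which invites the stronger reading. The document also does not say how finely age is recorded above 60, so the form of the age term must depend on the microdata.

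**Conclusion.** The concern holds, and the plan should be changed before the model is relied on. The omission and the lack of a reason are matters of text and are certain. It is equally certain that the planned model yields no age odds ratio.

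The amount of bias in the other odds ratios is not known. It depends on the age effect remaining after the 11 covariates. It is nil if risk is flat by age, or if age acts only through the included health and function variables. It could be material if a substantial direct age gradient remains. The claim is therefore that these odds ratios are open to confounding, not that they are biased by a given amount. It is best supported for arthrosis, incontinence and carrying difficulty.

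**What to change.** Add age to the covariate list in section 2.3 and to the survey-weighted logistic regression in section 2.4. Use the finest form the microdata allow: bands, or a continuous term with a check for non-linearity. Report the age odds ratio, and show the other odds ratios with and without age so that the reader can see what the adjustment does.

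If age was left out on purpose, for example because the health variables are seen as the routes by which it acts, state that reason in section 2.3 and still report the model with age as a sensitivity analysis.

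The cost is a few parameters on top of 13 and no new data collection. Intervals for variables correlated with age will widen slightly. Where health and function variables lie on the path from age to accidents, the age odds ratio is only the association that remains after them, and the text should describe it that way.

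### The glasses covariate puts people who cannot see at all in the same level as glasses wearers, so its odds ratio is not a pure glasses-use contrast

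*Combined protocol and SAP*

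**What the plan says.** Section 2.3 (Independent variables) lists 11 covariates. The only one related to vision is wearing "glasses (yes/cannot see at all, no), experiencing difficulty in carrying or holding items (no", a two-level variable: one level holds those who wear glasses and those who cannot see at all, the other holds everyone else. No reason for the grouping is given, no count of people without sight, and no analysis that separates them.

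On where the covariates come from, the same section says: "The independent variables included in the study are those available in the Türkiye Health" Survey, and that they were chosen from the literature as risk factors ("Survey. These variables were selected as risk factors based on the literature (5, 7, 19, 27-33"). Section 2.4 (Statistical Analysis) then fits survey-weighted models: "participants. Then, binary logistic regression analyses were employed to identify the risk factors". The odds ratio for this term will therefore be read as that of a candidate risk factor.

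The Introduction mentions vision twice, each time as impaired sight and not as glasses use: "2.7 times higher in individuals living with children, 2.3 times higher in visually impaired older" and, in a list of risk factors for falls, "and balance, dementia, impaired vision, arthrosis, diabetes, stroke, Parkinson's disease, and".

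**The concern.** A two-level covariate yields one odds ratio. Here the non-reference level mixes two groups that differ in the respect that matters: people whose sight may be fully corrected, and people with no sight. If the second group has a raised risk of home accidents, part of that risk is credited to glasses. The group's own association is not reported anywhere.

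What is at stake is the meaning of one row in the results table. A reader could not tell whether a ratio above 1 came from glasses wearers or from the few who cannot see, and people without sight, whose risk is of obvious interest in a paper on home safety, would have no visible estimate. Nothing here touches the outcome definition, and no effect on the other ten estimates is shown.

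**Working it through.** The plan states no sample size, group count or odds ratio for this term, so there is no figure to reproduce. What follows is an unadjusted illustration on the odds scale, because the model is logistic.

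**Inputs**
- Share who cannot see, b: 0.5-3% of the sample (assumption).
- Share wearing glasses, g: 40-70% (assumption).
- Odds ratio for people who cannot see against the no-glasses level, R: 2.3 (assumption; the number is borrowed from the Introduction, where it is a relative frequency for visually impaired people in general), and 4 (assumption).
- Odds ratio for glasses wearers against the no-glasses level: 1 (assumption).
- Risk in the no-glasses level, p0: 5% (assumption) to 38.6% (the Introduction's prevalence of at least one accident, which is not this study's injury outcome).

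**Step 1: share of the pooled level who cannot see.** s = b/(g+b).
- Smallest: 0.005/0.705 = 0.0071.
- Largest: 0.03/0.43 = 0.0698.

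**Step 2: pooled odds ratio.** The risk for people who cannot see is pb = R·o/(1+R·o), with o = p0/(1−p0). The pooled risk is (1−s)·p0 + s·pb. The pooling factor is the pooled odds divided by o. At the largest share, s = 0.0698:

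| R | p0 | pb | pooled risk | factor |
|---|---|---|---|---|
| 2.3 | 0.05 | 0.1080 | 0.0540 | 1.09 |
| 2.3 | 0.386 | 0.5912 | 0.4003 | 1.06 |
| 4 | 0.05 | 0.1739 | 0.0586 | 1.18 |
| 4 | 0.386 | 0.7155 | 0.4090 | 1.10 |

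At the smallest share, s = 0.0071, the same steps with R = 2.3 give 1.009 at 5% and 1.006 at 38.6%.

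The factor moves somewhat with the assumed glasses odds ratio. If that were 0.8 with R = 2.3 and p0 = 0.05, the wearers' risk is 0.0404, the pooled risk is 0.0404 + 0.0698 × (0.1080 − 0.0404) = 0.0451, and the factor is 0.0473/0.0421 = 1.12.

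**Step 3: what the pooled row hides.** In the first line of the table the two groups have odds ratios of 1 and 2.3, and the single reported figure is 1.09. At the smallest share it would be about 1.01. In neither case could a reader recover the 2.3.

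**Step 4: is a separate level workable?** For a 95% interval within a factor of 2 either side, against a large comparison group and without adjustment, n = D/[p(1−p)(ln 2/1.96)²], where D is the design effect and p the risk in that level. With (ln 2/1.96)² = 0.1251:
- p = 0.05: 1/(0.0475 × 0.1251), so 169 people at D = 1 and 337 at D = 2.
- p = 0.386: 1/(0.2370 × 0.1251), so 34 people at D = 1. This is optimistic, because 38.6% counts any accident.

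At the assumed shares, 169 people means a sample of about 169/0.03 = 5,633 to 169/0.005 = 33,800. The documents do not say how many respondents are aged 60 and above.

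**Step 5: does the file hold the response separately?** Elsewhere in section 2.3 slashes join graded answers, as in "fair, poor/very poor), presence of arthrosis (no, yes), urinary incontinence (no, yes), wearing" and "difficulty, some difficulty/considerable difficulty/cannot do at all), experiencing difficulty in". This suggests that the pooled glasses level is also a grouping of separate answers. It does not prove it.

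**The case against.** The strongest reply has three parts.

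**The plan calls the term glasses use, not visual impairment.** This stands. A reader might infer from the Introduction that the covariate is meant to stand for impaired sight, and that people with uncorrected poor sight in the no-glasses level therefore bias it. The plan never says so, and references 27-33 are not described. Non-wearers of every sight level belong in the comparison group of any wear/not-wear contrast. Only if the term is read as impaired sight does this matter. Suppose 25% of that level had uncorrected poor sight with an odds ratio of 2.3. At p0 = 5% among the rest, the level's risk is 0.75 × 0.05 + 0.25 × 0.1080 = 0.0645, and every ratio against it is multiplied by 0.0526/0.0689 = 0.76; at 38.6% the factor is 0.81. Pooling does not cause this, and recoding does not remove it.

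**The pooling effect is small.** This stands for the glasses contrast. A reader might infer serious distortion of the glasses odds ratio, but the documents give no counts that would support that, and the assumed ranges mostly point to a few per cent.

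**The category may be the survey's own.** This is possible, since the covariates are limited to what the survey offers. If so, the level cannot be split. That would explain the coding, but the odds ratio would still describe a mixed group and would need to be labelled as such.

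**Conclusion.** The point holds as a limited one. As coded, the odds ratio mixes glasses use with absence of sight, and it conceals any association for people who cannot see. That follows from the text of section 2.3 alone.

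Its size rests wholly on assumptions. With a glasses odds ratio of 1 and the shares above, pooling multiplies that ratio by at most about 1.06-1.09 when the odds ratio for people who cannot see is 2.3, and by 1.10-1.18 when it is 4. The larger benefit of separating the groups is that the second contrast can be seen at all.

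The documents do not support saying that the term is a failed measure of visual impairment, that the glasses estimate is badly biased, or that the authors certainly merged two answers. One of 11 covariates is affected. I would class this as a cheap improvement.

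**What to change.** 1. Check the survey file for whether *cannot see at all* is a separate response, and report its count.
2. If it is, code three levels: no glasses, glasses, cannot see at all. Before fitting, set a rule for when the third level is too sparse. If the rule is met, take that group out of the glasses contrast and report its count and accident frequency separately.
3. If it is not, label the row as the pooled category.
4. State in section 2.3 that, once separated, the term is interpreted only as glasses use and not as visual impairment.
5. If the file has an item on difficulty seeing (none is shown in the documents), that is the better vision covariate. It can be coded by function, as the carrying or holding item already is. Only this would deal with uncorrected poor sight among non-wearers, should impaired sight be of interest.

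The cost is one recode. Section 2.4 is in the past tense but the Results are blank, so at most one refit is needed. The drawbacks are that the separate level may be small and imprecise, and that the glasses odds ratio itself will probably change little.
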